### 1.2. Secondary Objectives

Secondary objectives of this study are to determine the number of patients in glucocorticoid-free remission and the change in prednisone dose compared to baseline at Week 16, after the open-label period (Period 1) of the study. Additional secondary objectives at both Week 16 and Week 28 are to demonstrate that sarilumab treatment is effective for reducing disease manifestation-specific metrics, for improving laboratory parameters, and for reducing cumulative prednisone dose. An important secondary objective is to demonstrate safety in this patient population.

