## **4. TREATMENT PLAN**

At Screening, vital signs will be obtained, a physical examination performed, and complete medical history obtained. **Routine clinical laboratory tests** (including a chemistry panel, complete blood count, urinalysis, spot urine protein and creatinine, C-reactive protein (CRP), erythrocyte sedimentation rate (ESR), urine pregnancy test), **sarcoidosis-related laboratory tests** (including angiotensin converting enzyme (ACE), total immunoglobulins (IgG), urine calcium, 25-hydroxy vitamin D, and **safety laboratory tests** (including serum pregnancy test for females, HIV test, hepatitis B test, hepatitis C test, and quantiferon test for tuberculosis) will be performed. An electrocardiogram and chest x-ray will also be obtained. At Baseline and Week 16, routine clinical laboratory tests and sarcoidosis-related laboratory tests will be repeated, and in addition the following tests will be performed at Baseline (and only repeated at Week 16 if abnormal at Baseline): pulmonary function tests, chest computed tomography, creatinine kinase (CK), aldolase, and lactate dehydrogenase (LDH). At Week 28, routine clinical laboratory tests and sarcoidosis-related laboratory tests will be repeated. At visits 3-11, vital signs, a physical examination, a medical history, and routine clinical laboratory tests will be obtained, urine pregnancy test for WOCBP. At Baseline, Week 16, and Week 28 the ePOST, global patient VAS, global physician VAS, HAQ, and FACIT-F will be assessed. Also at Baseline, Week 16, and Week 28, eight green

top tubes will be collected and processed for plasma and peripheral blood mononuclear cells, which will be stored at -80°C for future research.

During Period 1 (Baseline through Week 16), all subjects will receive 200mg of sarilumab subcutaneously every two weeks. During Period 2 (Week 16 through Week 28), half of the subjects who responded in Period 1 will receive 200mg of sarilumab subcutaneously every two weeks and half of the subjects will receive matching placebo in a double-blinded fashion.

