## 10. MEASUREMENTS

### 10.1 Primary and Secondary Outcome measures

*Primary endpoint:* The primary endpoint is the flare-free survival of sarilumab-treated patients compared to placebo-treated controls in the double-blind randomized withdrawal period (Period 2) from Week 16 to Week 28. Patients will be considered to have flared if they receive rescue medication including increased glucocorticoids, or if they discontinue the study treatment in order to start a different therapy.

*Secondary endpoints:* The following secondary endpoints will all be assessed at Week 16 and Week 28 compared to baseline as a paired analysis: the change in the extrapulmonary physician organ severity tool (ePOST) score (17 organs rated 0-6, for a total score range of 0-102) [16], the change in global score of sarcoidosis using a visual analogue scale (VAS) by both the patient and physician (distance in mm measured on a 10 cm line), the change in FACIT-F score (fatigue scale ranging from 0-52 with higher score meaning less fatigue), the change in the Health Assessment Questionnaire (HAQ), the change in prednisone dose, the change in serum angiotensin converting enzyme (ACE), serum immunoglobulin G (IgG) levels, serum calcium, urine calcium, and serum 25-hydroxy vitamin D (25-OH-vit D), the change in pulmonary function tests (FVC, FEV1, and DLCO), the change in ALT, AST, and alkaline phosphatase, the change in serum creatinine and urine protein levels, the change in the Sarcoidosis Activity and Severity Index for cutaneous sarcoidosis (7 parameters scored 0-4 for a total score range of 0-28) [17], the change in CK, aldolase, and LDH, and the change in size of sarcoidosis lesions (i.e. enlarged lymph nodes, hepatic nodules, pulmonary nodules) by CT imaging. For patients with known or suspected ocular involvement, the secondary endpoint of change in ophthalmology global assessment of ocular sarcoidosis using a visual analogue scale (VAS) (distance in mm measured on a 10 cm line) [18] will be assessed, as well as the change in any one or more of the following parameters: best corrected visual acuity (BCVA), slit lamp examination (including grading of anterior chamber cells), tonometry, dilated indirect ophthalmoscopy (including grading of vitreous cells and haze), optical coherence tomography (OCT) and OCT angiography, color fundus photography, and fluorescein angiography.

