# **12. STATISTICAL CONSIDERATIONS**

## **12.1 Statistical Design**

Patient characteristics including demographics, medical history, and concomitant medications will be summarized. The summaries will be done using descriptive statistics, eg, mean, standard deviation, median, minimum and maximum for quantitative values and counts and percents for qualitative variables.

The primary efficacy analysis of flare-free survival in Period 2 from Week 16 to Week 28 will use the intention-to-treat (ITT) population and will be assessed with Kaplan-Meier methods. **Patients will be considered to have flared in Period 2 if they receive rescue medication including increased glucocorticoids, or if they discontinue the study treatment in order to start a different immunosuppressive therapy.**

For Period 1, secondary endpoint variables will be treated as continuous and the values at Week 16 will be compared to Baseline values using Wilcoxon signed-rank tests. The number of patients in glucocorticoid-free remission at week 16 will be reported. Patients will be considered non-responders in Period 1 if they are unable to complete the glucocorticoid taper, receive rescue medication including increased glucocorticoids, or discontinue the study treatment in order to start a different therapy. For Period 1 secondary efficacy endpoints, non-responders will be included in the analysis only if their prednisone dose is equal to or less than the starting dose and stable for the 4 weeks preceding Week 16. The rationale for this is that patients who flare despite sarilumab therapy might be given high doses of steroids, thus improving their endpoints and falsely attributing the success to sarilumab. As a sensitivity analysis, we will also assess the secondary outcomes using the baseline observation carried forward (BOCF) for those patients deemed non-responders.

For Period 2, time to first flare will be compared using a 2-sided log-rank test. The proportion of patients in glucocorticoid-free remission at week 28 in sarilumab-treated patients compared to placebo controls will be analyzed using a Fisher's exact test. The remaining secondary endpoint variables will be treated as continuous and the values at Week 28 will be compared to Week 16 and to Baseline values using Wilcoxon signed-rank tests. We will not perform any corrections for multiple hypothesis testing due to the exploratory nature of this pilot study which solely aims to generate areas of potential future investigation.

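### Apart from flare and glucocorticoid-free remission, the Week 28 secondary endpoints get only paired tests (cumulative prednisone gets none), so the plan does not estimate sarilumab versus placebo on them

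*Combined protocol and SAP*

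**What the plan says.** Section 1.2 sets the Week 28 aim: "Additional secondary objectives at both Week 16 and Week 28 are to demonstrate that sarilumab treatment is effective for reducing disease manifestation-specific metrics", and likewise "for improving laboratory parameters, and for reducing cumulative prednisone dose". In Period 2 the responders are split, and "half of the subjects will receive matching placebo in a double-blinded fashion" (Section 4).

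Section 12.1 assesses flare-free survival by Kaplan-Meier methods with a two-sided log-rank test, and glucocorticoid-free remission at Week 28 by Fisher's exact test. Those are the only between-arm comparisons. For everything else it says: "The remaining secondary endpoint variables will be treated as continuous and the values at Week 28 will be compared to Week 16" and also to Baseline, by Wilcoxon signed-rank tests. Section 10.1 agrees: "The following secondary endpoints will all be assessed at Week 16 and Week 28 compared to baseline as a paired analysis". Neither section says whether the paired tests pool the arms or are run within each arm.

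Section 10.1 lists change in prednisone dose but not cumulative dose, and Section 12.1 names no cumulative-dose analysis.

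For Period 1, Section 12.1 restricts the use of data from non-responders, reasoning that "patients who flare despite sarilumab therapy might be given high doses of steroids, thus improving their endpoints". It gives no corresponding rule for Period 2. It waives multiplicity correction "due to the exploratory nature of this pilot study which solely aims to generate areas of potential future investigation".

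**The concern.** Period 2 is the only randomised, placebo-controlled part of the trial. On ePOST, patient and physician VAS, FACIT-F, HAQ, prednisone dose and the laboratory measures, the concurrent control goes unused. A pooled paired test mixes patients on drug with patients on placebo. Paired tests by arm ask whether each arm changed, and one significant result beside one non-significant result does not estimate the difference between arms.

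All patients taper prednisone up to Week 16, so some later movement common to both arms is possible. A paired test cannot separate such movement from a drug effect. What is at stake is how the Week 28 secondary results are read against an objective worded as demonstrating effectiveness.

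**Working it through.** **1. Inputs.** Section 12.3 gives 12 patients in Period 2, about 6 per arm, with expected flares of 85% on placebo (about 5 of 6) and 15% on sarilumab (about 1 of 6). It describes flare as restarting prednisone. The documents give no SD, drift or rescue effect for any secondary endpoint, so those below are assumptions. There is no stated figure for these endpoints to reproduce.

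**2. Shared drift, no drug effect.** Week 16 to Week 28 changes are taken as normal with SD 1, 6 per arm, exact two-sided tests at 0.05, 20,000 replicates.

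| Drift (SD) | Pooled signed-rank, p ≤ 0.05 | By arm: sarilumab significant, placebo not | Between-arm rank-sum |
|---|---|---|---|
| 0 | 4% | 3% | 4% |
| 0.25 | 11% | 5% | 4% |
| 0.5 | 32% | 10% | 4% |
| 1 | 85% | 23% | 4% |

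**3. Real effect, arms moving apart.** With changes of +0.5 and −0.5 SD (difference 1 SD), the pooled test is significant in 2.6% of trials and the rank-sum in 30%. With +1 and −1 SD (difference 2 SD), the figures are 0.5% and 83%.

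**4. Prednisone dose under the plan's own flare figures.** Assume that responders are off prednisone at Week 16 and that only flared patients are on it at Week 28. Zeros drop out of the signed-rank test, so k rises and no falls give p = 2/2^k.
- Pooled, 6 rises: 2/64 = 0.031.
- Placebo, 5 rises: 2/32 = 0.0625.
- Sarilumab, 1 rise: 2/2 = 1.0.

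The pooled result would signal a rise in dose in the very scenario where the drug works. None of the three measures the arm difference.

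**5. Cumulative prednisone, Week 16 to Week 28, compared between arms.** Five placebo patients and one sarilumab patient have a positive total, and six patients are tied at zero. The exact rank-sum p depends on where the one sarilumab total ranks among the six positive totals. From lowest to highest it is 0.015, 0.028, 0.041, 0.054, 0.067 and 0.113.

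**6. What a between-arm comparison can deliver.** The smallest two-sided rank-sum p at 6 v 6 is 2/C(12,6) = 2/924 = 0.002. The exact Hodges-Lehmann interval has 95.9% coverage and a median width of 2.7 SD.

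**7. Effect of rescue on observed values.** If rescue improves a flared patient's score by r SD, the expected observed difference is the true difference − (0.85 − 0.15) × r.

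| True difference | r | Expected observed difference | Rank-sum power |
|---|---|---|---|
| 1 SD | 0 | 1.00 | 30% |
| 1 SD | 1 | 0.30 | about 6% |
| 1 SD | 2 | −0.40 | sign reversed |
| 2 SD | 0 | 2.00 | 83% |
| 2 SD | 1 | 1.30 | 43% |
| 2 SD | 2 | 0.60 | 8% |

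Flares here are independent of the score. If instead exactly 5 of 6 and 1 of 6 flare and they are the worst scorers, the last two power figures become 65% and 25%.

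**The case against.** The paired analysis is a stated choice on which Sections 10.1 and 12.1 agree, in a study that calls itself an exploratory pilot. The main randomised question is compared between arms. Softer wording of the objective in Section 1.2 would remove part of the tension. All of this stands and limits the severity. It does not make a within-patient change answer a drug-versus-placebo question, and generating hypotheses about the drug also calls for an estimate of the arm difference.

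A reader might take 32% and 85% as false-positive rates of the planned tests. They are not. A signed-rank test asks whether values changed, and under drift they did. The figures are errors only if significance is read as a sarilumab effect. They also assume pooling, which the plan does not state, and a drift for which the documents give no source. The plan's own flare assumption has the arms diverging, not moving together.

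A reader might also infer that a between-arm test of observed values settles the matter. With about 5 of 6 placebo patients rescued, it does not: rescue can mask a difference or make placebo look better. Handling rescue is a choice of estimand that the plan has yet to make.

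Finally, the phrase about remaining variables might be stretched to cover cumulative prednisone. It is not on the Section 10.1 list, and a cumulative dose has no defined baseline value for a paired test.

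**Conclusion.** The point holds and should be fixed. Outside flare and glucocorticoid-free remission, the plan as written yields no sarilumab-versus-placebo estimate at Week 28, and one stated objective, cumulative prednisone, has no analysis. These conclusions come from the text and need no assumption.

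The size of a possible misreading rests on assumed SD-unit drifts. At 0.5 or 1 SD it is 32% or 85% if the arms are pooled and 10% or 23% if tested by arm, against about 4% for a between-arm test. The documents do not support the larger inference that the trial's efficacy conclusion is compromised: the primary endpoint is compared between arms and is unaffected.

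**What to change.** **In Section 12.1:**
- For endpoints already measured at Weeks 16 and 28 (ePOST, VAS, FACIT-F, HAQ, laboratory values), report the between-arm difference in Week 16 to Week 28 change as a Hodges-Lehmann estimate with exact interval. Give the rank-sum p as support and present the results mainly as estimation. Keep paired results, by arm, as descriptive.
- Compare cumulative prednisone from Week 16 to Week 28 between arms, and state that the steroid diary runs to Week 28 (the synopsis gives it no end date). This is the comparison least distorted by rescue, since restarted prednisone is what it counts. Report separately any flare that consisted of a switch to another therapy, which a prednisone total could miss.
- For the other endpoints, show rescue counts by arm and state that observed values can hide or reverse an arm difference. Add a sensitivity analysis that accounts for rescue, for example flare as worst rank, where the direction of benefit is clear.

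**Cost.** SAP wording, slightly different code and a minor protocol amendment, which Section 11.1 sends to the IRB. The amendment is needed to confirm that flared patients are still assessed at Week 28. No section says so, and the early-termination column of Section 9 lacks ePOST, VAS, FACIT-F and HAQ. Power stays low and intervals wide, as shown above.

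**Separately, a lesser point.** Section 10.1 lists PFTs, CT lesion size, CK, aldolase and LDH for Week 28, but Sections 4 and 9 do not schedule them then. The skin index and eye measures have no row in the calendar. Reconcile these by scheduling them or by removing them from the Week 28 list.

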## 12.3 Sample Size

The sample size for Period 1 of the trial of 15 patients was calculated based on the assumption that 80% of the patients will respond to open-label sarilumab, allowing for 12 patients to enroll in the randomized withdrawal Period 2 of the study. The sample size of 12 for Period 2 was calculated based on the assumption that 85% of the placebo group (roughly 5 out of 6) will flare (i.e. require reinitiation of prednisone) over the subsequent 12 weeks compared to 15% (roughly 1 out of 6) in the sarilumab group. This relative hazard of 0.20 gives a power of 80% with an alpha of 0.05 to detect a difference between treatment groups assuming Kaplan-Meier analysis. There is no published data on the use of sarilumab in sarcoidosis on which to base these assumptions. However, a parallel can be drawn between glucocorticoid-dependent sarcoidosis and glucocorticoid-dependent recurrent pericarditis, as they are both inflammatory and refractory to typical treatments. The latter condition has been studied with Anakinra, an interleukin 1 $\beta$  recombinant receptor antagonist [19]. In that study, 21 out of 21 patients (100%) had a complete response in Period 1 and were subsequently randomized to withdrawal during Period 2. In Period 2, 9 out of 10 (90%) patients receiving placebo had disease recurrence compared to 2 out of 11 patients (18%) receiving Anakinra. Although this is a different disease with a drug targeting a different inflammatory cytokine, there is precedent for a dramatic response in diseases like sarcoidosis using drugs like sarilumab. A sample size of 15 was deemed recruitable at Stanford after searching the Stanford medicine Research data Repository (STARR), which is a clinical data warehouse containing all patients seen at Stanford Hospital and Clinics. A search for patients between the ages of 18 and 75 who were given the diagnosis code for sarcoidosis on at least two separate occasions within the last year and who are currently on prednisone, yields 200 potential patients. Assuming half of these are coded correctly, and one-third of those truly have glucocorticoid-dependent, refractory disease, that leaves roughly 30 patients to screen, half of which we anticipate will be eligible for, and willing to participate in, the study. Our IRB will allow us to identify specific patients within STARR whom we can contact to determine their interest in the study.

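### Section 12.1 guards the Week 16 secondary endpoints against post-rescue values but gives no rule for the Week 28 tests, and does not say whether those tests are pooled or by arm

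*Combined protocol and SAP*

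**What the plan says.** Section 1.2 ties the Week 28 measures to a claim about the drug: "Additional secondary objectives at both Week 16 and Week 28 are to demonstrate that sarilumab treatment is effective for reducing disease manifestation-specific metrics".

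Section 12.1 treats the two periods differently.

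- **Period 1.** A main-analysis restriction applies: "non-responders will be included in the analysis only if their prednisone dose is equal to or less than the starting dose and stable". Stability is judged over four weeks before Week 16. A sensitivity analysis is added "using the baseline observation carried forward (BOCF) for those patients deemed non-responders". The stated reason: "patients who flare despite sarilumab therapy might be given high doses of steroids, thus improving their endpoints and falsely attributing the success to sarilumab". The status that triggers both safeguards is defined for that period only: "Patients will be considered non-responders in Period 1 if they are unable to complete the glucocorticoid taper", or if they are rescued or switch therapy.
- **Period 2.** The remaining secondary variables get one sentence: "the values at Week 28 will be compared to Week 16 and to Baseline values using Wilcoxon signed-rank tests". No exclusion, carry-forward or other rule for rescue follows. Intention-to-treat is named only for the primary analysis.

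A Period 2 flare is itself a change of treatment: "Patients will be considered to have flared in Period 2 if they receive rescue medication including increased glucocorticoids", or if they stop study treatment to start another immunosuppressive therapy. Section 12.3 assumes that "85% of the placebo group (roughly 5 out of 6) will flare" over 12 weeks, against 15% on sarilumab, and equates flaring with restarting prednisone.

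**The concern.** The plan identifies a specific bias, guards against it at Week 16, and then leaves it open at Week 28, where rescue is expected in half of the randomised patients. A placebo patient who flares at Week 20, is rescued and looks well at Week 28 would count as having kept the Week 16 benefit.

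At stake is the reading of the Week 28 disease scores and sarcoidosis laboratory tests, which Section 1.2 presents as evidence that sarilumab works. Because the plan does not say whether arms are pooled, the reader cannot tell in advance which way rescue would distort a result.

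**Working it through.** **Inputs.** 12 patients in Period 2 (Section 12.3), randomised 1:1 (Synopsis), so 6 per arm. Flare rates 85% and 15% (Section 12.3). In Period 1, 15 patients with 80% response (Section 12.3). Removal criteria from Section 4.2; visits from the Section 9 calendar.

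**1. The plan's own figure.** Expected flares = n × rate.
- Placebo: 6 × 0.85 = 5.1.
- Sarilumab: 6 × 0.15 = 0.9.
- Total: 6.0 of 12.

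This reproduces the plan's roughly 5 of 6 and 1 of 6. By chance alone, at least 4 of 6 placebo patients would be rescued with probability 0.176 + 0.399 + 0.377 = 0.953 (binomial, 0.85).

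**2. Comparison with Period 1.** Expected non-response is 15 × 0.20 = 3 of 15, or 20%. Rescue in Period 2 is 50% pooled, 85% in placebo and 15% in the sarilumab arm. The excess over Period 1 is therefore in placebo, and appears in the tests if arms are pooled or if placebo is tested alone.

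**3. Do rescued patients have Week 28 values?** Section 4.2 provides for removal by decision of the safety committee or by withdrawal of consent; flare is not listed. The calendar schedules ePOST, both VAS, FACIT-F, HAQ and the sarcoidosis laboratory tests at Week 28. So a rescued patient can supply these values, and nothing in Section 12.1 keeps them out.

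The documents give no flare timing; time since rescue could be anything from 0 to 12 weeks. If the placebo hazard were constant (an assumption), it would be −ln(0.15)/12 = 0.158 per week. The mean flare time among flarers would be 1/0.158 − 12 × 0.15/0.85 = 4.2 weeks, leaving about 7.8 weeks since rescue.

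**4. Direction of the distortion.**

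| Grouping of the signed-rank test | Expected share rescued | What rescue can do |
|---|---|---|
| Pooled | 6.0/12 = 50% | Credit sarilumab with the steroid effect |
| Sarilumab arm | 0.9/6 = 15% | Same, on a smaller share |
| Placebo arm | 5.1/6 = 85% | Hide loss of benefit on withdrawal |

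**5. Can the Period 1 rule simply be copied?** No.
- Excluding rescued patients leaves on average 0.9 placebo and 5.1 sarilumab patients. The placebo arm is empty with probability 0.85^6 = 0.377.
- The smallest two-sided signed-rank p-value is 2/2^n: 0.031 for n = 6 and 0.0625 for n = 5. A test within the sarilumab arm could reach 0.05 only if nobody in it flared, again probability 0.377.
- The Period 1 reference is the starting dose. A patient who restarted prednisone at or below that dose, and was stable for four weeks, would still be included.

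**6. Can the last pre-rescue value be carried forward?** Not for these endpoints. The calendar does not collect ePOST, VAS, FACIT-F, HAQ or the sarcoidosis laboratory tests at Weeks 18, 20 or 24. Unless an unscheduled visit took place, the last pre-rescue value is Week 16. Change from Week 16 is then exactly zero, and the patient is again recorded as having lost nothing.

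**The case against.** The strongest reply is that these are uncorrected secondary tests in a small study that Section 12.1 describes as an exploratory pilot. It adds that the plan is silent on rescued patients and nowhere says their values are used as observed. It also notes that within the sarilumab arm the expected share rescued (15%) is below the Period 1 non-response rate (20%).

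The last point stands: for patients still on sarilumab, rescue is not expected to be more common than in Period 1. The pilot label limits how much weight the tests can carry, but it is the plan's reason for omitting multiplicity correction. It does not explain guarding against a bias at Week 16 and not at Week 28.

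On silence, use of post-rescue values is an inference from the removal criteria and the calendar. The alternative is no better. If flared patients left early, the early-termination visit collects no ePOST, VAS, FACIT-F or HAQ, and those values would be missing with no rule.

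A reader might go further and infer that the difference between arms shrinks by some stated amount. The documents do not support this. No between-arm test of these continuous endpoints is planned, and neither the worsening at flare nor the recovery after rescue is given. A reader might also infer that all the Week 28 objectives are compromised. They are not: time to flare and glucocorticoid-free remission count steroid rescue as failure, and prednisone dose measures steroid use directly.

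**Conclusion.** The gap is real and should be closed before analysis. On the plan's own rates, about 6 of 12 patients would contribute Week 28 values taken after restarting prednisone, about 5 of them on placebo. This rests on the Section 12.3 flare rates and on flared patients staying to Week 28.

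The direction of the bias depends on a grouping the plan does not state, and its size cannot be derived from the documents. It concerns ePOST, both VAS, FACIT-F, HAQ and the sarcoidosis laboratory tests. The primary endpoint is untouched. Pulmonary function, CT and CK/aldolase/LDH have no Week 28 visit in the calendar, so for them the difficulty is absence of data. The effect is on interpretation of secondary results.

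**What to change.** In Section 12.1:

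1. Report and test Week 28 changes separately by randomised arm.
2. For patients who flared, keep post-rescue values out of the main analysis. Use the value from the flare assessment before rescue, if one was collected. If none exists, carry the Baseline value forward for the comparison with Baseline, as in the Period 1 sensitivity analysis, and assign a worst-rank score for the comparison with Week 16. Do not carry the Week 16 value forward.
3. Report as-observed Week 28 values as a sensitivity analysis, and keep prednisone dose as observed.
4. State how zero changes are handled. Carrying Baseline forward gives a change of zero, which the usual signed-rank test discards, so the median change over all patients in the arm should be reported beside the test.

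In Section 9, add a footnote saying that the assessments in the Unscheduled column also apply when a flare is identified at a scheduled visit.

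The cost is a few sentences and one footnote, plus these assessments at flares found on scheduled visits. The downsides are small: flare-visit values are earlier than Week 28, so follow-up differs between patients, and worst-rank scoring is conservative. No change to rescue or dosing is proposed.

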	
reduced to 40 mg daily by the end of week 3 at the clinician's discretion. Starting at week 4, all patients will begin a scheduled prednisone taper that will take place from week 4 until week 16.
 
Patients will be required to adhere to this tapering protocol. If a violation in the tapering schedule occurs, the patient will be deemed a nonresponder. Patients will be required to fill out a daily steroid diary to clearly document their daily prednisone intake. All attempts will be made to perform a pill count at each visit.
 
During Period 2 of the study (starting at Week 16), the patients that responded in Period 1 will be randomized to withdraw from sarilumab. Patients will be assigned in a blinded, 1:1 fashion to receive either sarilumab 200mg subcutaneously every two weeks or matching placebo.

SAMPLE SIZE	15 patients
STATISTICAL CONSIDERATIONS	
The sample size for Period 1 of the trial of 15 patients was calculated based on the assumption that 80% of the patients will respond to open-label sarilumab, allowing for 12 patients to enroll in the randomized withdrawal Period 2 of the study. The sample size of 12 for Period 2 was calculated based on the assumption that 85% of the placebo group (roughly 5 out of 6) will flare (i.e., require reinitiation of prednisone) over the subsequent 12 weeks compared to 15% (roughly 1 out of 6) in the sarilumab group. This relative hazard of 0.20 gives a power of 80% with an alpha of 0.05 to detect a difference between treatment groups assuming Kaplan-Meier analysis.
 
A sample size of 15 was deemed recruitable at Stanford after searching the Stanford medicine Research data Repository (STARR), which is a clinical data warehouse containing all patients seen at Stanford Hospital and Clinics. A search for patients

between the ages of 18 and 75 who were given the diagnosis code for sarcoidosis on at least two separate occasions within the last year and who are currently on prednisone, yields 200 potential patients. Assuming half of these are coded correctly, and one-third of those truly have glucocorticoid-dependent, refractory disease, that leaves roughly 30 patients to screen, half of which we anticipate will be eligible for, and willing to participate in, the study. Our IRB will allow us to identify specific patients within STARR whom we can contact to determine their interest in the study.

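### Week 28 is tested against Baseline in Period 1 responders only, so the change is selected on outcome and leans towards improvement relative to the treated cohort

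*Combined protocol and SAP*

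**What the plan says.** Section 10.1 says of the secondary endpoints: "The following secondary endpoints will all be assessed at Week 16 and Week 28 compared to baseline as a paired analysis". Section 12.1 gives the method for the continuous ones after Period 2: "the values at Week 28 will be compared to Week 16 and to Baseline values using Wilcoxon signed-rank tests". It does not say whether the arms are pooled, and it plans no between-arm test for these endpoints.

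Entry to Period 2 is restricted. The Synopsis says "the patients that responded in Period 1 will be randomized to withdraw from sarilumab", and Section 4 says "half of the subjects who responded in Period 1 will receive 200mg of sarilumab subcutaneously every two weeks", with the other half on placebo. Section 12.1 defines failure: "Patients will be considered non-responders in Period 1 if they are unable to complete the glucocorticoid taper", or if they receive rescue medication or stop study treatment to start another therapy. Section 12.3 expects 80% of 15 to respond, "allowing for 12 patients to enroll in the randomized withdrawal Period 2 of the study".

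Section 12.1 limits when non-responders enter the analysis and adds a sensitivity analysis carrying their Baseline value forward (BOCF). Both stand in the Period 1 paragraph, and their use at Week 28 is not stated. Section 1.2 nevertheless sets the aim of demonstrating effectiveness at Week 28 as well as at Week 16.

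**The concern.** A paired test against Baseline describes the treated population only if the patients with a later value are not chosen by how they did in between. Here they are: on the plan's own figures, the 3 of 15 who fail Period 1 are absent at Week 28. Disease activity plausibly drives both taper failure and the activity scores, so the patients lost would tend to be those with the worst change. Those who remain can then show a gain from Baseline without any drug effect.

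At stake is the Week 28 part of the Section 1.2 objective. A list of small p-values against Baseline could be read as sustained efficacy when part of the gain comes from the entry rule.

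**Working it through.** **Inputs from the documents.** Enrolled: 15. Assumed response: 80%. Assumed Period 2 flares: roughly 5 of 6 on placebo and 1 of 6 on sarilumab (Section 12.3). Starting prednisone: at least 10 mg daily (Section 3.1).

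**Inputs assumed.** The correlation (rho) between the course that decides Period 1 response and the Baseline-to-Week 28 change; zero mean change unless stated; exact two-sided signed-rank test at 0.05, so 2.5% nominal in each direction. The documents give none of these for the Week 28 tests.

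**1. The plan's own figure.** 15 × 0.80 = 12 enter Period 2, which reproduces. 15 − 12 = 3 do not.

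**2. Expected shift from selection.** If the best 80% on a standard normal latent course are kept, their latent mean is φ(0.84)/0.80 = 0.28/0.80 = 0.35 SD. The mean change among them shifts by rho × 0.35: 0.3 × 0.35 = 0.11, 0.5 × 0.35 = 0.18, 0.7 × 0.35 = 0.25 and 0.9 × 0.35 = 0.32 SD.

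**3. False improvement, no drug effect, 12 of 15 kept.** Rates from repeated simulations of 2,000 to 6,000 trials per setting, rounded:

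| rho | Shift (SD) | False improvement |
|---|---|---|
| 0 | 0 | no excess (about 2%) |
| 0.3 | 0.11 | 4% to 5% |
| 0.5 | 0.18 | 7% to 8% |
| 0.7 | 0.25 | 11% to 13% |
| 0.9 | 0.32 | 18% to 20% |

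False worsening falls below 1% for rho of 0.3 or more. If all 15 are kept with observed Week 28 values, false improvement is 2.2% to 3.1%. If only 60% respond (9 patients), it is 6.7%, 13.3% and 25.1% for rho of 0.3, 0.5 and 0.7.

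**4. Does BOCF repair it?** No. It gives non-responders a difference of zero, and the standard signed-rank test drops zeros. The simulated rejection rate was identical to that in responders only.

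**5. Prednisone dose.** Responders have completed the taper from at least 10 mg. If all 12 are below their starting dose at Week 28, p = 2/2¹² = 0.0005. On the plan's flare assumptions, 5 + 1 = 6 flare and 6 do not. If the 6 who flare return exactly to their starting dose (zero differences) and the other 6 are lower, p = 2/2⁶ = 0.031.

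**6. Is Week 16 a clean reference?** Take three visits with assumed pairwise correlation 0.5, no true change, 12 of 15 kept, and selection correlated 0.5, 0.7 or 0.9 with the Week 16 change from Baseline.

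- Week 28 v Baseline: shift +0.08, +0.12, +0.15 SD; false improvement 4.0%, 4.6%, 6.2%.
- Week 28 v Week 16: shift −0.07, −0.12, −0.15 SD; false worsening 3.9%, 5.1%, 7.2%.

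The two leans mirror each other. Patients picked for good status at Week 16 tend to drift back by Week 28.

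**7. Between randomised arms.** A rank-sum comparison among responders had a simulated two-sided type I error of at most about 4% in every setting, because both arms passed the same selection.

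**The case against.** Four points on the other side deserve weight.

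- *The size rests on assumptions.* Failure is settled by Week 16, while the outcome is measured 12 weeks later, after about half the patients have been switched to placebo. A correlation of 0.9 across measures as varied as vitamin D, HAQ and CT lesion size has no support in the documents. When selection acts only through the Week 16 value, the rate is about 4% to 6%. This stands: the upper figures are extremes.
- *The net direction is not fixed.* All patients are tapered, and 85% of the placebo arm is expected to flare, so true worsening may offset the lean; rescue steroids after a flare may add to it. This stands, but an offset is not a cure. If the whole group worsens by 0.2 SD, then at rho 0.5 and 80% response the observed mean worsening falls to 0.04 SD, and the test detects it in 2.9% of trials instead of 10.5%.
- *The plan calls itself an exploratory pilot.* Section 12.1 uses this to justify omitting multiplicity correction. It does not remove a systematic lean, and it sits badly with the Section 1.2 aim of demonstrating effectiveness.
- *The absence of non-responders at Week 28 is inferred.* It follows from the entry rule; the documents do not state outright that these patients leave.

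A reader might also infer that Week 16 is the one undistorted reference and that a Week 28 v Week 16 signed-rank test would suffice. Step 6 shows otherwise. Nor do the documents support carrying this point over to the primary log-rank test or the Fisher test, since both compare randomised arms.

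**Conclusion.** The concern holds for the Week 28 v Baseline tests. The sample is selected on Period 1 outcome, and relative to the whole treated cohort the change leans towards improvement whenever failure and the Week 28 change are correlated. At the planned 12 of 15 with no true change, false improvement is about 4% to 12% for assumed correlations of 0.3 to 0.7, about 20% at 0.9 and without excess at 0, against 2.5% nominal. It is larger if fewer respond. The correlation and the mean change are assumptions, so no single rate should be quoted as the size of the bias, and the net direction of the observed change cannot be predicted. Prednisone dose is the clearest case, because the entry rule largely produces the result. These are secondary endpoints, but they feed a stated objective and a change of wording removes the problem.

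**What to change.** In Sections 10.1 and 12.1:

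1. Drop the Week 28 v Baseline p-values. Show that change by arm as description only, labelled 'Period 1 responders only'.
2. Make the inferential Week 28 analysis the sarilumab v placebo comparison of change from Week 16 between randomised arms (rank-sum), in place of a pooled or within-group Week 28 v Week 16 test.
3. State how non-responders and values recorded after a flare are handled at Week 28. Rescue steroids can blur the between-arm contrast too, and the existing rule covers Period 1 only.

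In Section 1.2, align the Week 28 wording with this, so that effectiveness at Week 28 rests on the randomised comparison.

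The cost is wording. One set of p-values is lost. The between-arm test at about 6 per arm has low power: it can reach significance (smallest two-sided p = 2/924 = 0.002 with 6 v 6), but only for large differences.
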